4.4 Other Endpoint(s) Analysis

4.4.1 Achievement of EASI 75 response up to Week 8 (Day 56)

Generally, the EASI 75 response over time will be analyzed similarly to the analyses for Day 84 (Visit 7) but restricted to those approaches where the intercurrent event "use of rescue medication" is handled similary between Day 1 (Visit 3) and Day 84 (Visit 7) to have comparable estimates over time. The analysis will be done according to the exploratory estimand for all time points (refer to Section 1.1). In detail, the following analyses will be performed for all time points (refer to Table 4-1):

- PPS, B_2.1, B_2.2 ("use of rescue medication" is handled as non-response for all following time points),
- FAS, B_7.1 and B_7.2 ("use of rescue medication" is handled as non-response for all following time points).

In addition, an analysis over time will be performed on the PPS where rescue medication does not trigger the classification as non-responder at all to assess the effect of study intervention on top of topical AD medication:

• PPS, B_5.1 and B_5.2 ("use of rescue medication" is ignored for all time points).

For details with respect to data handling and the imputation strategy refer to Section 8.4.

The probabilities for EASI 75 response at Day 84 (Visit 7) by treatment and the difference between treatments as derived from the Bayesian analysis will be plotted including 95% credible intervals for all analyses as summarized in Table 4-1.

Furthermore, the probabilities for EASI 75 response over time by treatment and the difference between treatments as derived from the Bayesian analysis as described above will be plotted including 95% credible intervals for the following analyses in one plot (for numbers refer to Table 4-1):

- PPS, B_2.1 + B_2.2 and B_5.1 + B_5.2,
- FAS, B_7.1 + B_7.2.

The other binary efficacy endpoints will be analyzed similarly.

4.4.2 Percent change in EASI score over time

As for binary endpoints, the percent change in EASI score over time will be analyzed similarly to the analyses for Day 84 (Visit 7) but restricted to those approaches where the intercurrent event "use of rescue medication" is handled similary between Day 1 (Visit 3) and Day 84 (Visit 7) to have comparable estimates over time. In detail, the following analyses will be performed for all time points (refer to Table 4-2):

- PPS, C_2.1 and C_2.2 (values after first "use of rescue medication" are set to missing and imputed for the following time points),
- FAS, C_5.1 and C_5.2 (values after first "use of rescue medication" are set to missing and imputed for the following time points).

In addition, an analysis over time will be performed on the PPS where use of rescue medication is disregarded for analysis to assess the effect of study intervention on top of topical AD medication:

• PPS, C_3.1 and C_3.2 ("use of rescue medication" is ignored for all time points).

Furthermore, for both scenarios as described above, i. e.:

- 1. values after first "use of rescue medication" are set to missing for the following time points
 - (PPS: analysis C_2.3, FAS: analysis C_5.3),
- 2. "Use of rescue medication" is ignored for all time points (PPS: analysis C_3.3)

a mixed-effect repeated measurement model will be applied. This model will include the respective continuous efficacy endpoint as dependent variable. All post-dose data (without FU visit) will be included in the model. The model will include the respective baseline value as covariate, treatment group, visit and the interaction of visit and treatment group (visit*treatment group) as fixed effects. The covariance structure will be assumed to be unstructured, but the same for both treatment groups. The structure of the covariance matrix might be adapted, e. g. in case of convergence problems. The treatment difference (including 95% confidence intervals) at the planned end of treatment at Day 84 (Visit 7), as well as at the other time points, will be calculated by appropriate contrasts from the mixed-effect repeated measurement model.

Single subjects without any valid post-dose value in the treatment phase according to Section 8.4.1 (e. g. which discontinued treatment before first post-dose visit at Day 14 (Visit 4) due to lack of efficacy or took rescue medication at all visits until treatment discontinuation) will be included in the mixed model by using last observation carried forward for Day 14 (Visit 4) to avoid bias. Post-dose values from unscheduled visits or early discontinuation visits will be considered irrespectively of any time windows (but early discontinuation visits will only be considered if study intervention was not stopped earlier than 3 days ago). Otherwise, the baseline value will be carried forward.

Additionally for the same scenarios as for the mixed effect repeated measurement model, multiple imputation using linear regression will be performed using the multiple imputation procedure (PROC MI) from SAS based on the following variables: treatment, absolute EASI score at Day 1 (Visit 3), Day 14 (Visit 4), Day 28 (Visit 5), Day 56 (Visit 6), Day 84 (Visit 7). The fully conditional specification (FCS) method will be used in such a way that for each imputed continuous variable, all preceding variables will be considered. The seed will be 6345 and 50 imputations will be performed. Imputed values will be restricted to the range of possible values using the minimum and maximum options of SAS multiple imputation procedure (i. e. if values are imputed outside of the possible range, another value will be re-

drawn for imputation). The missing data pattern and variance information outputs for the multiple imputation will be presented in Section 10 of the CSR.

All participants from the PPS or FAS, respectively, will be included.

If the linear regression will not be possible for both treatment groups due to scarcity of data especially at later time points the imputation will only be performed for the zabedosertib group.

Subsequently, an analysis of covariance (ANCOVA) as described above will be performed by visit for all visits as planned.

The mean estimates for percent change of EASI score at Day 84 (Visit 7) by treatment and the difference between treatments as derived from the ANCOVA model or mixed model of repeated measures analysis as described above will be plotted including 95% confidence intervals for all analyses as summarized in Table 4-2.

Furthermore, the mean estimates for percent change in EASI score over time by treatment and the difference between treatments as derived from the ANCOVA model or mixed model of repeated measures analysis as described above will be plotted including 95% confidence intervals for the following analyses in one plot (for numbers refer to Table 4-2):

- PPS, C_2.1 + C_2.2 + C_2.3 + C_2.4 and C_3.1 + C_3.2 + C_3.3 + C_3.4,
- FAS, C_5.1 + C_5.2 + C_5.3 + C_5.4.

Other continuous end points will be handled similarly.

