6.9.2 Rescue Medication

In the event of a disease flare or AD symptoms defined as any worsening of AD to an vIGA \geq 3 requiring escalation of treatment confirmed by an investigator, which cannot be tolerated by the study participant, topical rescue medication as defined below may be used for a timeframe of several days at the discretion of the investigator. Before topical treatment for AD (= rescue medication) is initiated, the frequency of emollient use should be increased to try to control AD symptoms and efficacy assessments should be performed (see below and Section 8.1 [Unscheduled visit]).

Defined rescue medication for this study is the methylprednisolone aceponate (Advantan[®] cream). Only if Advantan cream is not available in the respective country, an alternative TCS with similar potency may be used (see WHO definition for potent corticosteroids group III, such as betamethasone, fluclorolone, desoximetasone, fluocinolone acetonide, budesonide, mometasone, beclomethasone, hydrocortisone aceponate). If TCSs are not tolerated or their use is not advisable, the topical TCIs pimecrolimus 1% (Elidel[®] cream) or tacrolimus (Protopic[®] 0.1% or 0.03% ointment) may be used.

The rescue medication is considered an auxiliary medicinal product (not an investigational product). The daily amount and frequency of application should be once daily for 1 week. If necessary, the duration of application may be extended to a maximum of 2 weeks. The use of rescue medication has to be documented in the CRF, providing information on product, dose, frequency and duration of therapy.

Topical rescue medication will be locally supplied/reimbursed by the sponsor during the study, including follow-up, according to the locally agreed process. Whenever possible, the efficacy assessments using the EASI, vIGA-AD and BSA affected by AD should be performed immediately before start of topical rescue therapy and at its end. Site visits

(scheduled or unscheduled) are therefore strongly recommended before start of rescue treatment.

If topical rescue medication is used, study intervention (zabedosertib or placebo) will be continued and study visits performed according to the SoA (see Section 1.3).

6.9.3 **Prohibited Medication and Therapies**

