4.2.4 Supplementary Analyses

Handling of use of rescue medication

The following supplementary analyses will be performed on the PPS to further assess the influence of rescue medication use on the EASI 75 response.

The analysis will be performed with a different handling of the following intercurrent event:

• Use of topical rescue medication: At Day 56 (Visit 6) or later (until Day 84 (Visit 7) or end of treatment if before Day 84 (Visit 7)): analyze study participant as non-responder (composite strategy)

Before Day 56 (Visit 6): disregard use of topical rescue medication (treatment policy strategy)

Use of rescue medication will be handled for supplementary analyses as outlined in the following:

The study participant is considered a non-responder in case of rescue medication use between the EOT visit and

- Baseline,
- 2 weeks after baseline,
- 4 weeks after baseline.

One additional analysis will be performed where rescue medication does not trigger the classification as non-responder at all to assess the effect of combined treatment of zabedosertib with topical AD medication.

If rescue medication does not trigger the classification as non-responder, the EASI 75 response will be based on the EASI scores collected after use of rescue medication.

Participants who take SoC medication or who discontinue study intervention due to lack of efficacy will still be counted as a non-responder for the time points after SoC use or discontinuation of study intervention due to lack of efficacy as described above.

The EASI score at time points after discontinuation of treatment due to other reasons not related to lack of efficacy or otherwise missing values will be imputed using "worst case" and last observation carried forward as described in Section 4.2.3. No multiple imputation approach using logistic regression will be performed for the supplementary analysis due to potential scarceness of participants continuing until Day 56 (Visit 6) without any rescue medication.

All other intercurrent events will be handled as described for the primary estimand.

Analysis on FAS

The EASI 75 response will be analyzed on the FAS according to the supplementary estimand (refer to Section 1.1). Imputation techniques in case of missing EASI 75 response information at Day 84 (Visit 7) will be as for the primary analysis.

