If the multiple imputation using linear regression as described above is based on less than 8 participants per treatment group the baseline EASI score and the EASI score at the previous visit will be used as independent variable in the linear regression model as described above. If there will not be sufficient participants to include one of the post-dose visits (Day 28 (Visit 5),

or – if not possible – Day 14 (Visit 4)) the linear regression model will only use the EASI score at baseline as independent variable. Then the model will be based on all participants with EASI score at baseline and EASI score at Day 84 (Visit 7). The EASI at Day 84 (Visit 7) could be imputed using worst post-dose observation carried forward after SoC use, discontinuation of study intervention due to lack of efficacy or use of rescue medication after Day 56 (Visit 6). The variables used in the regression model will be indicated below the output table.

If there is a participant with rescue medication use within the 7 days before the Day 56 (Visit 6) EASI score and missing EASI at Day 84 (Visit 7) which needs to be imputed the same procedure as described above (in case of less than 8 participants per treatment group) will be applied for that participant.

Imputed values below the minimum (0) or above the maximum (72) possible EASI score will be set to the minimum or maximum score.

Imputation according to the procedure defined above will be performed 50 times. All participants with EASI scores imputed using the linear regression method will be combined with the remaining participants (which will have the same values for each imputed dataset).

Then an analysis of covariance (ANCOVA) with the percent change from baseline in the EASI score at Day 84 (Visit 7) as dependent variable will be applied for each imputed dataset. The model will include treatment group as fixed effect and the EASI baseline value as covariate. The results from the model will be combined by Rubin's rule using SAS MIANALYZE procedure. The treatment difference (including 95% confidence intervals) at Day 84 (Visit 7) will be presented.

As a "worst case" scenario the analysis will be repeated by imputing all missing EASI scores at Day 84 (Visit 7) by carrying forward the worst post-dose EASI score (refer to Section 8.4.3 for details).

Furthermore, the analysis will be repeated by imputing all missing EASI scores at Day 84 (Visit 7) using last observation carried forward (refer to Section 8.4.3 for details).

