As for the binary endpoints supplementary analyses with respect to the time point after which rescue medication use leads to setting the subsequent values to missing will be performed as described for the binary endpoints in Section 4.2.4. The analysis will be similar to the main analysis but considering rescue medication use for analysis starting from Day 1 (Visit 3) or not at all. These analyses handle the rescue medication use in a similar manner over time. Thus, a mixed effect repeated measurement model will be applied in addition assuming the values are missing at random; and furthermore multiple imputation based on linear regression including all participants will be performed with subsequent ANCOVA analysis (for details refer to Section 4.4.2 and 8.4.3).

The analyses described above will be repeated on the FAS with exception of the main analysis (see Table 4-2). This approach will not be applied due to potential scarceness of participants without use of rescue medication in the 7 days before EASI scores at early time points before Day 56 (Visit 6). Furthermore, the analysis disregarding the use of rescue medication will not be performed on the FAS.

Table 4-2 summarizes the analyses for the percent change in EASI score at Day 84 (Visit 7).

Table 4-2 Main, sensitivity and supplementary analyses for the secondary endpoint percent change from baseline in EASI at Day 84 (Visit 7)

Analysis set	Analysis type	After "Use of rescue medication"	After "Use of SoC / discontinuation due to lack of efficacy"	After "Discontinuatio n due to other reasons" or missing values	No. of analysis for continuo us endpoint
	Main	Worst post- dose observation carried forward at/after Day 56 (Visit 6)	Worst post-dose observation carried forward	Multiple imputation using linear regression	C_1.1 (Main)
	Sensitivity	Worst post- dose observation carried forward at/after Day 56 (Visit 6)	Worst post-dose observation carried forward	Worst post-dose observation carried forward	C_1.2 (Sensiti- vity 1.1)
		Last observation carried forward at/after Day 56 (Visit 6)	Last observation carried forward	Last observation carried forward	C_1.3 (Sensiti- vity 1.2)
	Supplemen tary	Worst post- dose observation carried forward after Day 1 (Visit 3)	Worst post-dose observation carried forward	Worst post-dose observation carried forward	C_2.1 (Supple- mentary 1.1)
		Last observation carried forward after	Last observation carried forward	Last observation carried forward	C_2.2 (Supple- mentary 1.2)

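### When data are scarce, SAP 4.4.2 imputes missing values in the zabedosertib arm only but keeps the two-arm ANCOVA, which can bias supplementary analyses C_2.4 and C_5.4

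*SAP*

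**What the plan says.** SAP 4.4.2 describes a multiple imputation by fully conditional specification, "based on the following variables: treatment, absolute EASI score at Day 1 (Visit 3), Day 14 (Visit 4" and the later visits, with every PPS or FAS participant included. SAP 4.3.2 introduces the same analysis in the same terms: "multiple imputation based on linear regression including all participants will be performed with subsequent ANCOVA analysis".

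Section 4.4.2 then adds an exception. If the linear regression is not possible for both groups because of sparse data, "especially at later time points the imputation will only be performed for the zabedosertib group". The next sentence reads: "Subsequently, an analysis of covariance (ANCOVA) as described above will be performed by visit for all visits as planned". That ANCOVA is defined in 4.3.2, with treatment as a fixed effect and baseline EASI as covariate. Section 4.4.2 goes on to plot the treatment difference with 95% confidence intervals for every analysis in Table 4-2. It closes with "Other continuous end points will be handled similarly", which carries the rule over to BSA and Peak Pruritus.

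No readable sentence says how placebo participants with missing values enter the ANCOVA under the exception, or that the contrast is dropped. For details, 4.3.2 also points to Section 8.4.3, which is blacked out in the public copy.

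**The concern.** Read as written, the exception gives the two arms different estimands. Zabedosertib is summarised over everyone, with values after rescue, systemic standard of care or discontinuation imputed. Placebo is summarised over those with a value that was not set to missing. In C_2.4 and C_5.4 every value after first rescue from Day 1 is set to missing. Protocol 6.9.2 permits rescue for worsening to vIGA 3 or more, "requiring escalation of treatment confirmed by an investigator, which cannot be tolerated by the study participant". The placebo participants still observed at Day 84 are therefore likely to be those who did better. C_3.4 ignores rescue and is less exposed.

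The exception also differs from how the SAP handles scarcity elsewhere. For C_1.1, with fewer than 8 participants per group, the model steps back to an earlier visit and finally "the linear regression model will only use the EASI score at baseline as independent variable", with no arm singled out. For the supplementary EASI 75 analyses, multiple imputation is dropped altogether, "due to potential scarceness of participants continuing until Day 56 (Visit 6) without any rescue medication". In 4.4.2 there is no number behind the trigger, and the imputed arm is always zabedosertib, whichever arm is sparse.

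At stake is interpretation. C_2.4 and C_5.4 are plotted with the mixed-model results C_2.3 and C_5.3. A disagreement produced by the rule could be read as fragility of the drug effect.

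**Working it through.** **Plan's own figure.** The only stated design figure is power of at least 90% with 38 versus 19 evaluable, response rates 0.49 and 0.16, Beta(1,1) priors and a posterior threshold of 90% (SAP 5). Exact enumeration over the two binomials gives 91.0%, so it reproduces. The present point does not depend on it; it supplies the arm sizes used below.

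**Direction and size from first principles.** Let *p* be the fraction of placebo participants missing at Day 84. Let *d* be the mean percent change in the missing minus that in the observed, so *d* > 0 if the missing did worse.

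- Mean over all placebo = observed mean + *p·d*.
- So the observed placebo mean is *p·d* lower (better) than the mean over all placebo.
- If imputation recovers the zabedosertib mean, and ignoring the baseline covariate, the contrast (zabedosertib minus placebo) shifts by **+*p·d***, which is against zabedosertib. If *d* = 0 there is no shift.

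**Simulation A, restricted to trials where the fallback would plausibly fire.** All inputs are assumed, because the documents give no rescue rate, SD or visit correlation:

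- 38 versus 19 participants; baseline EASI mean 28, SD 10, minimum 16.
- Placebo percent change −20/−28/−35/−38 at Days 14/28/56/84 (sensitivity −10/−15/−20/−22); true difference 0, −15 or −25.
- SD 25 or 35; AR(1) correlation 0.75 (sensitivity 0.5).
- Monotone missingness after rescue, either dependent on the last percent change or unrelated to outcome (10% versus 25% per interval).
- Kept: trials with 3 to 7 observed placebo values (mean 5.2 to 5.8) and at least 8 zabedosertib values at Day 84; 600 to 700 trials per setting, 8 imputations each.

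Bias is the contrast minus the full-data contrast, in percentage points (Monte Carlo SE 0.4 to 0.8):

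| Handling | Rescue follows response (28 settings) | Missingness unrelated (6 settings) |
|---|---|---|
| Zabedosertib imputed only | +6.6 to +18.5 | +0.2 to +3.1 |
| Pooled imputation with treatment as a variable | −1.5 to +1.8 | −3.6 to −1.0 |
| Observed cases in both arms | about 0 to +5 | – |

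Examples: at SD 25 with moderate dependence, full data −25 and fallback −14; at SD 35, −24 and −6. With no true effect the fallback contrast was +7 to +18.

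The formula agrees. Taking 5.5 observed of 19 (midpoint of 5.2 and 5.8), *p* = 1 − 5.5/19 = 0.71. Shifts of 6.6 and 18.5 then imply *d* = 6.6/0.71 ≈ 9 and 18.5/0.71 ≈ 26 points, against assumed SDs of 25 and 35. That is a plausible gap between rescued and unrescued participants.

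**Simulation B, fixed missing fractions.** Assumed SD 35, correlation 0.7 between Day 56 and Day 84, worse participants more often missing; 1,500 trials per scenario, 10 imputations. Each cell shows the mean contrast for a true difference of 0, then of −20:

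| Missing (zabedosertib / placebo) | Placebo observed | Full data | Both arms imputed | Observed cases | Zabedosertib imputed only |
|---|---|---|---|---|---|
| 30% / 30% | 13 | 0.4; −19.0 | 0.2; −19.0 | 0.9; −18.1 | 10.5; −9.1 |
| 30% / 60% | 8 | 0.2; −19.3 | −0.3; −19.5 | 8.2; −10.9 | 17.6; −1.8 |
| 50% / 70% | 6 | 0.0; −19.0 | −0.4; −19.5 | 5.6; −12.5 | 20.8; 2.4 |
| 40% / 80% | 4 | 0.2; −18.9 | −0.4; −19.4 | 13.1; −5.3 | 25.7; 6.7 |

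Only the last two rows have fewer than 8 placebo values. There the fallback is off by 20.8 to 25.6 points from full data. Part of that comes from unequal missingness, since observed cases are off by 5.6 to 13.6. The one-arm rule adds 12.0 to 15.2 on top (for example 20.8 − 5.6 = 15.2; 6.7 − (−5.3) = 12.0). Imputing both arms removes nearly all of it.

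**The case against.** The case on the other side has real content.

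- **Redaction.** Section 8.4.3 may state how placebo enters or suppress the contrast. This stands as a caveat. But 4.4.2 says the ANCOVA runs as planned, so the two sections would still need aligning.
- **Trigger.** Listing treatment as a variable suggests a pooled model. Such a model fails on the placebo side only when placebo has essentially no values, and then there is no contrast to bias. Under a by-arm model, Day 84 on four earlier scores has 5 parameters, so 6 or 7 values technically suffice and a 3-to-7 trigger is too generous. A further simulation, again on assumed inputs, was therefore limited to 2 to 5 observed placebo values with response-dependent rescue. The fallback was about 11 to 26 points less favourable to zabedosertib than full data, while pooled imputation or observed cases stayed within about 7. The narrower trigger does not remove the problem. How often it would fire is unknown, and that part of the objection stands.
- **Scope.** C_2.4 and C_5.4 are two of 17 analyses in Table 4-2 of an exploratory study. The same rescue scenario is handled symmetrically in C_2.1 to C_2.3 and C_5.1 to C_5.3, and the likely bias cannot favour the drug. All true; it limits the weight of the point but does not justify the rule.
- **Inconsistency.** A specific exception may override the general statement in 4.3.2, and other analyses may have other scarcity rules. Fair. The fault is the one-arm treatment itself, not a contradiction between sections.

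**Conclusion.** The concern holds. On the readable text, the scarcity rule yields a between-arm contrast in which missing data are handled differently by arm. The direction is against zabedosertib if rescue tracks poor response. The size is illustrative: about 7 to 19 points with 3 to 7 observed placebo values, and larger (up to about 26) with heavier placebo loss or fewer observed values. If missingness is unrelated to outcome it is 0 to 3 points. These figures rest on assumed SDs, correlations and rescue mechanisms, are conditional on the rule firing, and assume 8.4.3 does not say otherwise. The consequence is confined to C_2.4, C_5.4 and their BSA and pruritus counterparts, with C_3.4 less exposed. It is worth correcting because it is cheap to correct. Confidence is medium.

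**What to change.** In SAP 4.4.2:

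1. Delete the zabedosertib-only fallback and handle both arms in the same way.
2. State that the imputation is one pooled model with treatment as a variable. If a by-arm model is meant, say so and apply the same step-back to both arms, as for C_1.1.
3. Replace the undefined trigger with a number. The 8 per group already used in 4.3.2 would serve; a pooled model may not strictly need it, but it makes the rule decidable before unblinding.
4. Where the imputation cannot be fitted at a visit, do not report the imputed contrast there and rely on the planned mixed model (C_2.3, C_5.3). A plain observed-case contrast is not a safe substitute when placebo loss is much heavier, as Simulation B shows.
5. Apply the same text to BSA and Peak Pruritus. If Section 8.4.3 already does this, align 4.4.2 with it.

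The cost is one or two sentences. A supplementary estimate at a late visit may go unreported. With few placebo values the pooled model borrows its slopes largely from the zabedosertib arm, which should be noted under the output.
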